6. GENERAL ANALYSIS DEFINITIONS

6.1 TREATMENT(S)

Treatments are not randomized. Different dose levels of ezabenlimab monotherapy and ezabenlimab / BI 754111 combination therapy will arise in two dose-finding parts (Part I and Part II) and there is only one dose level in expansion part (Part III). Data for Part I and II will be presented for all dose cohorts separately. Data of Part III will be displayed separately for different cohorts (cohort A to D).

For Part I and II, the initial trial medication (i.e. dose level) assigned at the beginning of the first treatment cycle will be used as label of the analysing treatment.

Table 6.1: 1 Definition of analysing treatment periods for safety analysis

Analysing Treatment Period	Start Date	Stop Date
Screening	Date of informed consent	Date/time of the first administration of trial treatment-1
On-treatment	Date/Time of the first administration of trial treatment	Date of the last administration of trial treatment + 30 days
Follow-up	Date of the last administration of trial treatment + 31 days	Date of the last contact or death, or DBL date, whichever comes first

Note: a 30-day residual effect period (REP) is defined for this trial.

For safety analyses, adverse events (AEs) will be classified to one of the following time periods: “Screening”, “On-treatment” or “Follow-up”. This will be applied for all adverse events. It is indicated in the protocol Section 7.3.4 that the residual effect period of this trial is 30 days, and thus AE reported within 30 days of the last trial medication will be considered on treatment. Detailed rule for assigning AEs to these time periods are listed below:

- If the date of informed consent \leq AE onset date $<$ date/time of first administration of ezabenlimab or BI 754111, then the AE is assigned to “Screening”;
- If date/time of first administration of ezabenlimab or BI 754111 \leq AE onset date \leq date of last administration of ezabenlimab or BI 754111 + 30 days, then the AE is assigned to “On-treatment”;
- If AE onset date $>$ date of last administration of ezabenlimab or BI 754111 + 30 days, then the AE is assigned to “Follow-up”

6.2 IMPORTANT PROTOCOL DEVIATION

A protocol deviation (PD) is important if it affects the rights or safety of the study patients, or if it can potentially influence the primary outcome measurements in a non-negligible way. Patients with important PDs that could potentially impact the evaluation of the primary endpoints will be excluded.

A list of important PDs is given in Table 6.2: 1 below. Important PDs will be reviewed at Medical Quality Review Meetings (MQRMs) conducted periodically during the trial. A list of protocol deviations will also be discussed at the Report Planning Meeting (RPM).

If a detected important PD cannot be categorized in any of the following table, another important PD category will be defined in MQRMs or RPMs. The decision whether a patient will be excluded from the analysis will be made at the final RPM prior to DBL.

Table 6.2: 1 Important protocol deviations

Category / Code		Description	Requirements	Excluded from	Automatic/ Manual
A		Entrance criteria not met			
A1		Inclusion criteria not met			
A1.1		Deviation from Inclusion criterion (IN) 1. Of full age (according to local legislation) at the time of signing of the informed consent form (ICF)	IN 1 not met	None	Automatic
A1.3		Deviation from IN 4. Patients with measurable lesions according to RECIST v1.1	IN 4 not met	None	Automatic
A1.4		Deviation from IN 6. Eastern Cooperative Oncology Group (ECOG, R01-0787) performance status (PS): 0 to 1 at screening	IN 6 not met	None	Automatic
A1.5		Deviation from IN 2. Women of childbearing potential (WOCBP) with negative serum pregnancy test at screening and men able to father a child, who agree to use highly effective methods of birth control per ICH M3 (R2) that result in a low failure rate of less than 1% per year when used consistently and correctly. A list of contraception methods meeting these criteria is provided in the patient information. The requirement of contraception does not apply to women of no childbearing potential but they must have an evidence of such at screening	IN 2 not met	None	Automatic
A1.6		Deviation from IN 5. Conditions specific to respective part of the trial described in protocol	IN 5 not met	None	Automatic
A2		Exclusion criteria met			
A2.1		Deviation from Exclusion criterion (EX) 1. Major surgery (major according to the investigator's assessment) performed within 12 weeks prior to study entry or planned within 12 months after screening, e.g. hip replacement	EX 1 met	None	Automatic

Table 6.2: 1 Important protocol deviations (Continued)

Category / Code	Description	Requirements	Excluded from	Automatic/ Manual
A2.2	Deviation from EX 2. Patients who must or wish to continue the intake of restricted medications (see Section 4.2.2.1) or any drug considered likely to interfere with the safe conduct of the trial	EX 2 met	None	Automatic
A2.3	Deviation from EX 3. Previous treatment with study medications in this trial	EX 3 met	None	Automatic
A2.4	Deviation from EX 4. Any investigational or anti-tumour treatment within 4 weeks or 5 half-life periods (whichever is shorter) prior to the initiation of trial treatment	EX 4 met	None	Automatic
A2.5	Deviation from EX 6. (Part II and III only) Prior treatment with anti-LAG-3 agents	EX 6 met	None	Automatic
A2.7	Deviation from EX 5. Any unresolved toxicities from prior therapy greater than Common Terminology Criteria for Adverse Events (CTCAE) Grade 1 at the time of starting study treatment with the exception of alopecia and Grade 2 neuropathy due to chemotherapy	EX 5 met	None	Automatic
A2.8	Deviation from EX 7. Patients with lung cancer that have epidermal growth factor receptor (EGFR) mutations or anaplastic lymphoma kinase (ALK) rearrangements, unless disease has progressed following available EGFR or ALK targeted therapy	EX 7 met	None	Automatic
A2.9	Deviation from EX 8. Presence of other active invasive cancers other than the one treated in this trial, with the exception of resected/ablated basal or squamous-cell carcinoma of the skin or carcinoma in situ of the cervix, or other local tumours considered cured by local treatment	EX 8 met	None	Automatic
A2.10	Deviation from EX 9. Untreated brain metastasis(es) that may be considered active. Patients with previously treated brain metastases may participate provided they are stable (i.e., without evidence of PD by imaging for at least 4 weeks prior to the first dose of trial treatment, and any neurologic symptoms have returned to baseline), and there is no evidence of new or enlarging brain metastases	EX 9 met	None	Automatic
A2.12	Deviation from EX 10. Inadequate organ function or bone marrow reserve as demonstrated by the following laboratory values:	EX 10 met	None	Automatic
A2.13	Deviation from EX 11. Any of the following cardiac criteria:	EX 11 met	None	Automatic
A2.14	Deviation from EX 12. History (including current) of interstitial lung disease or pneumonitis within the last 5 years	EX 12 met	None	Automatic
A2.15	Deviation from EX 13. History of severe hypersensitivity reactions to other mAbs	EX 13 met	None	Automatic
A2.16	Deviation from EX 15. Immunosuppressive corticosteroid doses (>10 mg prednisone daily or equivalent) within 4 weeks prior to the first dose of study treatment	EX 15 met	None	Automatic

Table 6.2: 1 Important protocol deviations (Continued)

Category / Code	Description	Requirements	Excluded from	Automatic/ Manual
A2.17	Deviation from EX 16. Active autoimmune disease or a documented history of autoimmune disease, except vitiligo or resolved childhood asthma/atopy	EX 16 met	None	Automatic
A2.18	Deviation from EX 17. Active infection requiring systemic treatment (antibacterial, antiviral, or antifungal therapy) at start of treatment in this trial	EX 17 met	None	Automatic
A2.19	Deviation from EX 18. Known history of human immunodeficiency virus (HIV) infection. Test results obtained in routine diagnostics are acceptable if done within 14 days before the informed consent date	EX 18 met	None	Automatic
A2.21	Deviation from EX 14. History of severe hypersensitivity reactions to the ingredients of study drug	EX 14 met	None	Automatic
A2.22	Deviation from EX 19. Any of the following laboratory evidence of hepatitis virus infection. Test results obtained in routine diagnostics are acceptable if done within 14 days before the informed consent date	EX 19 met	None	Automatic
A2.23	Deviation from EX 20. Chronic alcohol or drug abuse or any condition that, in the investigator's opinion, makes him/her an unreliable trial patient, unlikely to complete the trial, or unable to comply with the protocol procedures. However, in Part III Cohort C, patients with past chronic alcohol abuse are allowed	EX 20 met	None	Automatic
A2.24	Deviation from EX 21. Women who are pregnant, nursing, or who plan to become pregnant during the trial. Women who are nursing can be enrolled if they stop nursing. In this case, the patient cannot resume nursing even after discontinuation of study treatment.	EX 21 met	None	Automatic
B	Informed consent			
B1	Informed consent not available/not done	Informed consent date missing	TS	Automatic
B2	Informed consent too late	Informed consent date was after the initiation of treatment	None	Automatic
C	Trial medication			

Table 6.2: 1 Important protocol deviations (Continued)

Category / Code	Description	Requirements	Excluded from	Automatic/ Manual
C1.1	Non-compliance with ezabenlimab or BI 754111 administration per protocol	Incorrect trial medication dose taken or wrong dose schedule; (e.g. delay, infusion time, program) decision at MQRM	None	Automatic and manual
C1.2	Continuation/Discontinuation of trial medication not following the protocol	Decision at MQRM	None	Automatic and manual
D	Concomitant medication			
D1.1	Prohibited medication use	Review concomitant medications for prohibited medication use; also refer to Section 4.2.2.2 of the protocol	None	Manual
E	Study Specific			
E1	Incorrect study procedures performed	Any deviation from protocol not defined above deemed important to document in study report by trial team.	Discussion at MQRM/ RPM	Manual

Note: MQRM – Medical and Quality Review Meeting;

6.3 SUBJECT SETS ANALYSED

Screened Set:

This patient set includes all patients who have signed the informed consent. The screened set will be used for patient disposition tables.

Treated Set (TS):

This patient set includes all patients who were documented to have received at least one dose of ezabenlimab or BI 754111. The TS is used for both efficacy analysis and safety analyses.

[figure not shown]
MTD set:

This patient set includes all patients who were documented to have received at least one dose of ezabenlimab or BI 754111 in part I and part II and were not replaced for the MTD determination. The MTD evaluation set will be used for the primary analyses of DLTs and

MTD determination. The list of replaced patients will be provided by the Clinical Trial Lead no later than the final RPM and should be attached to the decision log, if applicable.

PK Analysis Set (PKS):

This patient set includes all patients in the TS which provide at least one evaluable observation for at least one [REDACTED] and no PK relevant protocol deviation. PKS is used for statistical PK analysis, if applicable.

6.5 POOLING OF CENTRES

The section is not applicable.

6.6 HANDLING OF MISSING DATA AND OUTLIERS

No imputation will be performed on missing efficacy data. Missing or incomplete AE dates are imputed according to BI standards. Missing data and outliers of PK data are handled according to [2].

Incomplete date of histological diagnosis, start/end date of previous systemic chemotherapy and previous radiotherapy are imputed as first date of its month or January first if day part or both month and day part is missing respectively.

If the day of the start date of subsequent systemic therapy/subsequent radiotherapy is missing, then the first date of its month will be imputed unless this leads to a date before the stop date of study medication. In this case the stop date of study medication +1 day will be imputed.

If day and month, or day and month and year are missing, it will be distinguished whether the start date of subsequent systemic therapy/subsequent radiotherapy is required [REDACTED] or for other descriptive statistics:

- For [REDACTED] duration of response: If only the year is reported, January first of this year will be imputed unless this leads to a date before the stop date of study medication. In this case the stop date of study medication +1 day will be imputed. [REDACTED]

[REDACTED] Additionally, all imputed start dates of subsequent anti-cancer therapy/subsequent radiotherapy should be before death date, if available.

- For descriptive statistics: Dates will not be imputed if more than only the day of the date is missing.

No other handling of missing data is planned.

6.7 BASELINE, TIME WINDOWS AND CALCULATED VISITS

Baseline values will be the measurements taken most recently prior to first administration of study drug.

For the laboratories not only the examination date but also time is recorded, examination time has to be taken into account when defining baseline. That is, a laboratory value on the same date as the first study drug administration is considered as baseline value if and only if the time of laboratory value is before or the same as the time of study drug administration. If any of these times is missing and the date of laboratory assessment is equal to the date of first drug administration, then the laboratory assessment will be considered as according to protocol, i.e. as prior to first study medication.

Study day will be calculated relative to the date of the first administration of study drug. The day prior to first administration of study drug will be “Day -1” and the day of first administration of study drug will be “Day 1”; therefore “Day 0” will not exist.

[figure not shown]
In order to identify whether consecutive imaging time points are missing for a given patient, a nominal time point (i.e. Week 6, 12, 18 ... etc.) will be assigned to each and every image. This is achieved by creating windows for every radiological response assessment. These windows are defined in Table 6.7: 1.

Table 6.7: 1 Nominal time points and windows for imaging

Nominal time point (weeks from start of study medication)	Due date of scans (days)*	Window (days)
6	43	1 to \leq 64
12	85	65 to \leq 106
18	127	107 to \leq 148
24	169	149 to \leq 200
33	232	201 to \leq 263
42	295	264 to \leq 326
51	358	327 to \leq 389
9 week interval

* The date of the first dose of study medication is Day 1

If a patient does not have an image in one of the windows described above, the patient will be said to have missed an assessment for that time point.

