3.3.4.1 Withdrawal from trial treatment

An individual patient is to be withdrawn from trial treatment if:

- The patient wants to withdraw from trial treatment, without the need to justify the decision.
- The patient needs to take concomitant drugs that interfere with the investigational product. Refer to Section [4.2.2.2](#) for permitted and prohibited concomitant medications.
- The patient can no longer be treated with trial medication for other medical reasons (such as surgery, AEs, other diseases, or pregnancy). Refer to Section [4.1.4](#) for AEs that require treatment discontinuation.

Proprietary confidential information © 2021 Boehringer Ingelheim International GmbH or one or more of its affiliated companies

- The patient has repeatedly shown to be non-compliant with important trial procedures and, in the opinion of both, the investigator and sponsor representative, is not willing or able to stick to the trial requirements in the future.
- The patient experiences unequivocal PD by RECIST v1.1 and/or iRECIST.
- The patient completes 1 year of treatment. If the patient is benefiting clinically at 1 year, he/she may continue after a case-by-case review with the sponsor.

Given the patient's agreement, the patient will undergo the procedures for the end-of-treatment (EOT) visit and follow up as outlined in the [Flow Chart](#) and Section [6.2.3](#). For all patients the reason for withdrawal from trial treatment (e.g. AEs) must be recorded in the CRF. These data will be included in the trial database and reported.

During the dose finding part, patients withdrawn for a reason other than having a DLT or patients who miss more than one visit during MTD evaluation period may be replaced after discussion in the SMC if the information that needed to be collected during that visit is not available and makes the patient non-evaluable for the PK analyses or safety parameters (including evaluation for DLTs).

Patients who come off trial due to a DLT will not be replaced.

If a patient should become pregnant during the trial, the treatment with BI 754091 and BI 754111 must immediately be stopped. The patient will be followed up until delivery or termination of pregnancy (see Section [5.2.7.9](#) for information on pregnancy forms). The data of the patient will be collected and reported in the eCRF until the last patient's last visit and any events occurring thereafter will be reported in the BI drug safety database.

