5. ASSESSMENTS

5.1 ASSESSMENT OF EFFICACY

5.1.1 Tumour assessments

The tumour response will be evaluated according to RECIST Version 1.1 ([R09-0262](#)) and iRECIST ([R17-0923](#)). The overview of iRECIST will be found in Appendix [10.6](#).

The assessment by the Investigator and/or the local radiologist will be the basis for continuation or discontinuation of the trial in an individual patient (in addition to safety). The baseline imaging must have been performed within 4 weeks prior to treatment with the trial medication and the Investigator will record the target and non-target lesions in the eCRF. The same method of assessment and the same technique must be used to characterise each reported lesion at baseline and during treatment. Lesions in previously irradiated areas may not be used as target lesions. Tumour assessments will be performed at screening (as close as possible to the treatment start and no more than 28 days before the start of study treatment), every 2 cycles (6 weeks \pm 5 days) for the first 6 months, then every 3 cycles (9 weeks \pm 5 days) thereafter, and at the EOT visit (if not performed within the previous 4 weeks).

If a patient discontinues trial medication for a reason other than PD, the tumour assessment according to RECIST and iRECIST will be performed according to standard of care until the last follow-up needed according to the protocol (PD, death, lost to follow-up, end of the trial).

Patients will be allowed to stay on treatment in the case of initial radiological PD, if the Investigator feels that it is in the patient's best interest, and the patient provides an additional consent. If a patient is considered to be confirmed progressive disease according to iRECIST (iCPD), the patient may still continue to receive treatment if the Investigator and sponsor agree that the patient is deriving clinical benefit, and the patient provides an additional consent.

Copies of CT/MRI/PET scan data will be collected by the sponsor for later radiomics assessment. It is planned to explore the potential for enhanced and improved baseline and on-treatment markers/ patterns of early efficacy based on comprehensive quantitative CT metrics, i.e. radiomics features, assessed in standard-of-care medical imaging data.

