6.2.3.3 Follow up visits for PFS (extended follow-up period)

Additional follow-up visits for PFS after the 30-day safety follow-up visit will only be performed for patients in Part III who did not progress on treatment. These will be performed once every 12 weeks at least (by telephone or in person) until PD.

The follow-up period for PFS will end at the earliest if one of the following events is met:

- Disease progression
- Start of a new anti-cancer therapy
- Death
- Withdrawal of consent
- Lost to follow-up
- End of whole trial as specified in Section [8.6](#)

Proprietary confidential information © 2021 Boehringer Ingelheim International GmbH or one or more of its affiliated companies

The following will be obtained and/or performed during the follow-up visits for PFS.

- Date of contact
- For each reportable serious adverse event / AESI, the investigator should provide the information with regard to concomitant medication and the medication administered to treat the adverse events on the appropriate CRF pages and the SAE form including trade name, indication and dates of administration
- Treatment and date with any subsequent anti-cancer therapy (including surgery and radiotherapy) including the name and type of the anti-cancer drug and/or best supportive care (if applicable)
- Outcome (date of and reason for death [if applicable], in case the patient had PD the actual date of PD shall be recorded)

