7.5.2.2 Other secondary endpoints in Part III

Duration of response according to RECIST Version 1.1 as assessed by the Investigator

Duration of response is defined as the duration from the date of first documented PR or CR according to RECIST Version 1.1 as assessed by the Investigator to the date of PD or death. Duration of response will be summarized descriptively by quartiles with 95% confidence interval (based on the Greenwood's method) calculated from Kaplan-Meier estimate. Kaplan-Meier plots will also be produced. Duration of objective response will use the censoring rule defined in below Table 7.5.2.2:1

[figure not shown]
Table 7.5.2.2:1 Censoring rules and determination of date of event or censoring for duration of response

[figure not shown]
Situation	Outcome (event or censored)	Date of outcome
No other anti-cancer therapy		
Alive and not progressed, no missed radiological assessments window*	Censored	Date of last radiological assessment
Alive and not progressed, one or more consecutively missed radiological assessments window*	Censored	Date of last radiological assessment prior to missed radiological assessments
Progressed, no radiological assessment window* prior to progression	Event	Date of radiological assessment of progression
Progressed, but one or more consecutively missed radiological assessments window* prior to progression	Censored	Date of last radiological assessment prior to missed radiological assessments
Death but no progression, no missed radiological assessment window* prior to death	Event	Date of death
Death without progression, but one or more consecutively missed radiological assessments window* prior to death	Censored	Date of last radiological assessment prior to missed radiological assessments
Initiation of subsequent anti-cancer therapy		
Subsequent anti-cancer therapy started before progression or death, no missed radiological assessments window* prior to start of subsequent anti-cancer therapy	Censored	Date of last radiological assessment before initiation of subsequent anti-cancer therapy

[figure not shown]
* Windows for radiological assessments are defined in [Table 6.7: 1](#)

[figure not shown]
Disease control according to RECIST Version 1.1 as assessed by the Investigator

Disease control is defined as a BOR of CR, PR or SD. Disease control rates will be presented with exact 95% Clopper-Pearson CIs.

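### SAP imaging windows run on at 9 weeks with no off-treatment rule, so DoR can be censored in responders who meet the protocol's follow-up requirements; SAP 7.4 must be reconciled at the same time

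*SAP*

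**What the plan says.** **Windows.** SAP Table 6.7:1 gives 63-day windows from the week-33 scan on and closes with the entry "9 week interval", with no end point. The rule below the table has one condition, "If a patient does not have an image in one of the windows described above", and when it is met the assessment for that time point counts as missed. Neither mentions end of treatment.

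**Censoring.** SAP Table 7.5.2.2:1 treats the case "Progressed, but one or more consecutively missed radiological assessments window* prior to progression" as censored, dated at "Date of last radiological assessment prior to missed radiological assessments". A death after a missed window is handled the same way. One missed window is enough.

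**Follow-up in the protocol.** The 6- and 9-weekly scans are defined in treatment cycles. When a patient stops for a reason other than progression, Protocol 5.1.1 says that "the tumour assessment according to RECIST and iRECIST will be performed according to standard of care". Extended follow-up in Part III starts after the 30-day visit, and Protocol 6.2.3.3 says of its visits: "These will be performed once every 12 weeks at least (by telephone or in person) until PD". The date of any progression is to be recorded there.

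**Stopping without progression is planned.** Protocol 3.3.4.1 lists as a reason to stop: "The patient completes 1 year of treatment". Continuation is possible case by case if the patient benefits.

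**Post-EOT data.** SAP 7.4 says that response data obtained after EOT, or after a new anti-cancer therapy starts, are not used, and extends this to every endpoint built on response data. SAP 5.2.2 and 7.5.2.2 define DoR up to progression or death.

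**The concern.** A missed-assessment rule should detect departures from the imaging schedule that applies to the patient. After EOT this one measures against a schedule that the protocol no longer imposes. A responder who does everything asked can have an empty window, and a documented progression or death then becomes a censored observation dated back to an earlier scan.

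Those exposed are responders who stop without progression, including long responders who complete a year. Cohorts have about 35 patients (30 was planned for Cohort E, since cancelled), so responders are few and each lost event counts. Losing late events leaves the Kaplan-Meier tail resting on treatment-period data and can make responses look more durable than they were. Whether this happens would depend on local scanning practice, which the protocol does not fix.

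**Working it through.** **Inputs.** Due days and window limits: SAP Table 6.7:1. 30-day visit at 30 to 37 days after EOT: Protocol 6.2.3.2. Contacts every 12 weeks (84 days) after that: Protocol 6.2.3.3. EOT scan not needed if one was done in the past 4 weeks: Protocol 6.2.3.1. *Assumption for steps 2 to 6:* off-treatment scans occur only at the minimum contacts. The documents neither state nor exclude this.

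**1. Reproduce the grid.** Due day = 1 + 7 × week. Upper limit = midpoint of neighbouring due days, rounded down. Week 33: 1 + 231 = 232; (232 + 295)/2 = 263.5, so 263. All seven due days and limits reproduce. The next windows are 390–452, 453–515 and 516–578.

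**2. Gap to the first contact.** From EOT: 30 + 84 = 114 to 37 + 84 = 121 days. If the last scan was up to 28 days before EOT, the gap extends to 121 + 28 = 149 days.

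**3. Chance of an empty window at the first contact.** Let the last scan fall on day p (1 to 63) of a 63-day window and the next come g days later. No window is missed only if p + g ≤ 126.
- g = 114: p ≤ 12, so 12/63 = 19% escape and 51/63 = 81% miss one.
- g = 121: p ≤ 5, so 5/63 = 8% escape and 92% miss one.
- g ≥ 126: all miss one.

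**4. Enumeration over stop days.**
- EOT on days 150 to 379, last scan at EOT: 194/230 = 84%. Last scan 0 to 28 days earlier: 6,436/6,670 = 96.5%. With the 30-day visit 7 days late these become 93% and 99%.
- On-treatment scans on the due days, with an EOT scan only where required: 87–95% for stops on days 85 to 365, and 81–92% for later stops.

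**5. Third contact.** This is at least 114 + 84 + 84 = 282 days after the last scan. Three scans can cover at most the next three windows, which requires p + 282 ≤ 252. That is impossible, so 100% have an empty window by then.

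**6. One-year completer.** Last scan day 358 (window 327–389), EOT day 365, first contact 365 + 114 = day 479 (window 453–515). Window 390–452 is empty, so progression found at that contact is censored at day 358. Treatment stops on days 358 to 366 with EOT up to 7 days later put the first contact on days 472 to 494, with the same result.

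**7. More frequent scans.** A step of 63 days or less cannot jump a 63-day window. For stops on days 200 to 1000, scans every 6, 8 or 9 weeks from the last scan give no missed window. Before day 200 the windows are narrower, so 9-weekly scans are not always safe: scans on days 90 and 153 leave 107–148 empty.

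**8. Tolerating one missed window.** Two consecutive empty 63-day windows need a gap of at least 127 days. With the 30-day visit on day 30, the share censored at the first contact falls to 0% (last scan at EOT) or 12% (0 to 28 days earlier).

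**9. Interaction with SAP 7.4** (event after EOT, before new therapy):

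| 7.4 bar | Grid after EOT | Progression | Death |
|---|---|---|---|
| kept | kept | not used | event, or censored if a window is empty |
| kept | ended | not used | event |
| lifted | kept | censored if a window is empty | censored if a window is empty |
| lifted | ended | event | event |

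Changing the grid alone recovers no progression; lifting the bar alone leaves progression exposed to the windows.

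**The case against.** The strongest objection is that the 12-weekly contact is not a scan schedule. It may be a telephone call, it is a minimum, and imaging is set by standard of care. A reader might infer that every responder followed to the protocol minimum is censored at the last treatment scan. The documents do not support that. The percentages hold only if scans are as sparse as the contacts, and even then 19% can pass the first contact without a missed window (step 3). This stands. What also stands is that no off-treatment interval is fixed, so compliance does not protect a patient from the rule.

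Second, SAP 7.4 discards progression after EOT before any window is consulted. A reader might infer that repairing the grid restores those events. It does not. But the grid still acts on deaths, and the bar itself conflicts with the DoR definition. It also sits badly with SAP 6.6, which imputes subsequent-therapy dates after treatment stop for DoR, and with the progression dates collected in extended follow-up.

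Third, much of the loss comes from the one-window threshold, not the grid alone (step 8). This stands: the mismatch does not bite equally at every tolerance.

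Fourth, one-year responders need not stop. Those who continue by agreement stay on 9-weekly scans and are not exposed.

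**Conclusion.** The concern holds in a conditional form. The SAP has no off-treatment rule for imaging windows, and its censoring table can turn a documented progression or death in a compliant responder into a censored observation. The size runs from nil, with scans at least every 9 weeks (for stops from day 200), to about 81–97% with an empty window by the first contact if scans follow only the minimum contacts, and up to 99% with the latest 30-day visit. The actual share cannot be known from the documents, because standard-of-care imaging is not specified.

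While the SAP 7.4 bar stands, the practical effect of the grid is mainly on deaths after EOT. The underlying fault is that three texts disagree: SAP 7.4, SAP Tables 6.7:1 and 7.5.2.2:1, and Protocol 5.1.1 with 6.2.3.3.

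Only DoR is affected, a descriptive Part III secondary endpoint in a trial without formal testing. A reader might extend this to ORR; the mismatch acts only through DoR censoring, so ORR is untouched. The point should be settled before database lock but does not threaten the primary result.

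**What to change.** Change the three texts together:

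1. **SAP 7.4:** state that, for DoR, progression and death after EOT and before any subsequent anti-cancer therapy count as events.
2. **SAP Table 6.7:1:** end the 9-week grid at EOT.
3. **SAP Table 7.5.2.2:1:** after EOT, judge missed assessments only against the follow-up schedule then in force. The first interval runs to the first extended follow-up contact (30 days plus 12 weeks, with an allowance), followed by 12-weekly intervals with an allowance. State that an interval with only a telephone contact does not by itself censor a documented progression or death.

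Keep the current grid as a sensitivity analysis, so that readers can see how far DoR depends on the rule.

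The cost is SAP wording and reprogramming of the window derivation; no scans are added. The downside is less precise progression dates off treatment: about 12 weeks between contacts and about 16 weeks from EOT to the first contact (114/7 = 16.3), and longer if the last scan preceded EOT. The sensitivity analysis shows how much this matters.
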